7. STUDY INTERVENTION

WP1: no intervention will be administered.

WP2: ET is the treatment that will be administered in the feasibility RCT. It aims to allow the social care needs of prisoners to be met through an integrated, person-centred, trauma-informed intervention. It is a manualised, structured programme that usually includes three core elements of screening, assessment, and social care coordination. In this study, screening will occur before randomisation (Section 6.1), with individuals allocated to the intervention or social care as usual. Assessments will then be conducted with prisoners in the intervention group post-randomisation (Section 6.3), and those with higher-level social care needs will receive social care coordination, whilst those with lower-level social care needs will be given tailored advice and signposting.

Care coordination involves ET workers coproducing care plans with prisoners and/or their carers, family members, or peers. These care plans consider placement in the prison (e.g., adapted cell, healthcare wing, vulnerable prisoner wing) and the support required. All domains of the Care Act are considered, including adaptations to cells and other parts of prisons (e.g., handrails, hygiene equipment, meal trays); coordination of peer support; necessary changes to the regime; support with maintaining personal relationships; and supplementary details of personalised care. The ET workers then coordinate across the complex systems of health, local authority, prison, and third sector organisations to deliver on care plans. A core part of the role of the ET worker is therefore to liaise with health, prison, and local authority staff, making referrals where appropriate, and

aiming to ensure prisoner needs are met (including via improved communication). ET workers act as advocates for the person in prison, including by referring for, feeding into, and attending the Care Act Assessment conducted by the local authority. They also liaise with prison authorities, whose responsibilities include the adaptation of the prison environment for social care.

Signposting to appropriate resources involves providing the participants with tailored advice and information about social care services available to them. These might include (but are not limited to) helplines, healthcare services, or peer support. Information will be developed in consultation with the PPIE panel and individual prisons, and provided in both verbal and written formats.

8. SAFETY MONITORING

8.1 Definitions

Term	Definition			
Adverse Event (AE)	An AE is an unfavourable or unintended disease, sign, or symptom that is temporally associated with the intervention, whether or not it is related to that intervention.			
Adverse Reaction (AR)	An AE that, in the opinion of the CIs, has the potential to be related to the intervention (i.e., its relationship to the intervention cannot be ruled out).			
Serious Adverse Event (SAE)	 A SAE is an untoward response that: results in death is life-threatening requires hospitalisation or prolongation of existing hospitalisation results in persistent or significant disability or incapacity consists of a congenital anomaly or birth defect Other events may be considered SAEs if they jeopardise the participant or require an intervention to prevent one of the above consequences. 			
Serious Adverse Reaction (SAR)	A SAE that, in the opinion of the CI, is believed with reasonable probability to be due to the intervention, based on the information provided.			

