1.5 Assessment and Management of Risks relating to this study

The risk of harm in this study is small, as activities will take place with assenting and consenting participants who have the capacity to understand the situation, and in a regulated environment (a prison, with prison staff aware of the research activities). Nevertheless, we acknowledge that participants may have mental disorders or other vulnerabilities and so might become distressed during research activities, and that their reasons for being in prison may include a propensity for violence. We have considered how to respond in the unlikely event of serious distress or threats.

Risks to Participants

There is a possibility that participants might experience discomfort or distress during workshops, feasibility RCT activities, or interviews. Participant Information Sheets (PIS) that describe ethical rights as well as the relevant research activities will be given to participants to help prepare them and minimise burdens and risks as far as possible. All activities will be carried out by experienced, trained researchers and staff, in conjunction with robustly trained experts by experience where possible. Researchers and staff will be aware of the sensitivities surrounding the activities and will carefully choose their approach to prioritise the comfort and ease of participants.

If a participant becomes distressed, researchers will draw on the approach outlined in Jefferson and Holloway (50), who advise that their role is one of emotional containment. For the workshops and interviews, this will involve offering participants the option to take a short break, and being guided by them as to whether to continue with the session. Researchers will have training to aid them in this decision. If a participant becomes significantly upset, researchers will adhere to the study safeguarding protocol. The consent process will make it clear that if a participant tells the researcher that they intend to harm themselves or someone else, confidentiality will be broken and relevant services will be informed immediately. Researchers who conduct interviews with people in prisons are also obligated to report the following and will make this clear to prospective participants in the PIS:

- Behaviour that is against prison rules
- Information that either indicates a risk or harm to the participant or others
- Information on previously undisclosed illegal acts or plans to commit a new crime

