8.2 Recording and Reporting

The safety reporting period will commence at the point of consent and end at the final study visit. The intervention (ET and signposting) is extremely low risk and therefore unlikely to result in AEs or SAEs. However, as participants are people with social care needs, it is possible that AEs, SAEs, and other safeguarding concerns unrelated to the intervention may arise. The ET workers and the researchers will record the dates and details of any concerns and incidents in a Safeguarding Log. The ET worker or researcher will then notify the CIs, who will review the log and, utilise their experience and judgement to determine if there is a causal relationship between the incident and the study (i.e., if it is an AR or SAR) and if further action is needed. This includes determining if the incident needs to be escalated as an SAR. Actions decided and taken will be recorded in the Log.

If an incident is determined to be an AR or SR, it must be entered into REDCap within 24 hours of the research team first becoming aware of it, even if not all information is available at the time of

reporting. The sponsor will be automatically notified when an SAE is entered. Change in condition and new follow-up information should be entered on the digital PenCTU SAE resolution form as soon as it is available or at least within 24 hours of the information becoming available.

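### Sections 8.1 and 8.2 contradict each other on what adverse events and reactions are judged against, so distress caused by research procedures is classified differently depending on which is followed

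*Protocol*

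**What the plan says.** **Protocol 1.5.** Under Risks to Participants, one risk is named: "There is a possibility that participants might experience discomfort or distress during workshops, feasibility RCT activities, or interviews". If a participant is significantly upset, "researchers will adhere to the study safeguarding protocol".

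**Protocol 8.1.** An AE is an unfavourable event "temporally associated with the intervention, whether or not it is related to that intervention". An AR is an AE that "has the potential to be related to the intervention". A SAR is a serious adverse event (SAE) that "is believed with reasonable probability to be due to the intervention". The SAE row begins "A SAE is an untoward response that" and lists outcomes without mentioning the intervention. Research procedures appear in none of the four definitions.

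**Protocol 8.2.** The safety period runs from consent to the final study visit. ET workers and researchers log all concerns and incidents. The chief investigators then "determine if there is a causal relationship between the incident and the study (i.e., if it is an AR or SAR". An incident judged to be an AR or an SR must be entered in REDCap within 24 hours. SR is not defined in 8.1 or in the list of abbreviations.

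**Protocol 8.3.** AEs, SAEs and safeguarding concerns go into the Safeguarding Log, the chief investigators assign causality, and safety information goes to the DMEC and TSC. All SAEs are reported to PenCTU and the sponsor.

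**Protocol 9.2.** Adverse events are to be summarised descriptively. The section does not say that the Safeguarding Log will be summarised.

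**The concern.** The risk the protocol expects comes from research activities, yet the AE and AR definitions refer only to the intervention. Section 8.2 uses a wider reference, the study, and presents it as meaning the same thing. A person applying 8.1 and a person applying 8.2 can therefore give one episode different labels.

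The label has consequences. It decides whether the 24-hour REDCap requirement applies and whether the event is among those summarised under 9.2. The trial is meant to judge the acceptability of its design and its measures (section 2.1), and distress caused by an assessment is direct evidence on both. If the definition has nothing to attach to in the control arm, an AE table carried forward to the full trial could show a difference between arms that the wording created.

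**Working it through.** The protocol gives no figure to reproduce here. The check is to apply each section, as written, to the same episode.

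**Inputs**
- 76 randomised, 38 per arm (9.1); 1:1 allocation to intervention or social care as usual (6.3).
- Order of events: consent, ET screen and baseline assessments, then randomisation (6.3).
- Outcome assessments at baseline, day 42 and day 90 in both arms (6.5).
- Safety period from consent to final study visit (8.2).

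**How the definitions nest.** In 8.1 an AR is a subset of AEs. An event that is not an AE under 8.1 therefore cannot be an AR under 8.1, whatever its cause.

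**Non-serious distress caused by an outcome interview**

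| When and in whom | Reading 8.1 literally | Reading 8.2 |
|---|---|---|
| Baseline, before randomisation | No intervention exists: not an AE, so not an AR | Inside the safety period and caused by the study: AR |
| Day 42 or 90, control arm | No intervention received: not an AE, so not an AR | AR |
| Day 42 or 90, intervention arm | AE, since relatedness is not required; AR only if a link to ET or signposting cannot be ruled out | AR |

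**What follows from each label**
- REDCap entry within 24 hours: required on the 8.2 reading in all three rows. On the 8.1 reading it is not triggered in the first two rows and may not be in the third.
- AE summary in 9.2: included on the 8.2 reading in all three rows, since an AR is an AE. On the 8.1 reading only the third row is included.

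**Serious events.** The SAE row makes no reference to the intervention and 8.3 has all SAEs reported, so recognising an SAE does not depend on the conflict. Calling it a SAR does: 8.1 asks about the intervention, 8.2 about the study.

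**Size of the gap in 8.1**
- Randomised participants with no intervention to serve as time reference: 76 − 38 = 38, and 38/76 = 50%.
- In addition, every participant between consent and randomisation. Consent is taken in two stages (6.1, 6.2), and 8.2 does not say which one opens the safety period, but both precede randomisation.

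**Effect on counts by arm.** Suppose k such episodes occur at follow-up in each arm. The literal 8.1 reading gives k AEs in the intervention arm and 0 in the control arm; the 8.2 reading gives k and k. This holds for any k above zero. The protocol gives no distress rate, so k itself cannot be estimated.

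**The case against.** The strongest reply is that nothing is lost. A reader might infer from 8.1 that research-related distress cannot be classified or counted at all, and the protocol does not support that. Sections 8.2 and 8.3 require concerns and incidents to be logged from consent onwards, whatever the arm or cause, and expect events unrelated to the intervention. Every entry is reviewed by the chief investigators, and safety information reaches the DMEC and TSC. Section 8.2 also supplies a route to classification, and serious events are recognised independently of the intervention.

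It can be added that causality is assigned centrally by the chief investigators or their delegate, with 8.2 as the working instruction, so opposite classifications may be rare in practice. One could read temporal association generously, as meaning within the trial period. Acceptability does not rest on the AE table alone either: process-evaluation interviews cover outcome measures and trial design (6.7), and withdrawal reasons and reasons for uncollected data are recorded (6.8, 9.3).

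Most of this stands, and it limits the point to inconsistent classification. It does not remove it. The log captures the event, but 8.2 makes REDCap entry turn on the AR label, and 9.2 summarises adverse events. The generous reading of timing is not what 8.1 says, and it would leave the conflict over AR and SAR causality untouched.

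**Conclusion.** The point holds as an internal contradiction. Section 8.1 judges events against the intervention; section 8.2 judges them against the study, from consent, and equates the result with AR or SAR. Research-related distress will be recorded, but its status as AE or AR, its 24-hour REDCap entry and its appearance in the AE summary depend on which section is followed.

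On a literal reading, the 8.1 AE definition has no reference point for 38 of 76 randomised participants (50%) and for everyone before randomisation. AE counts could therefore differ by arm as an artefact. This rests on reading 8.1 as written and on the planned 1:1 split. The number of events affected is unknown. No between-group testing is planned, so the damage would be to the descriptive safety record and to what it tells the designers of the full trial. The matter is modest, but it concerns rules that staff must apply from the first consent, and it is not one to leave to a statistical analysis plan.

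**What to change.** 1. In 8.1, define an AE as any untoward occurrence in a consented participant during the safety reporting period, in either arm, and state which of the two consents opens that period.
2. Record relatedness as two separate items: to the intervention (ET or signposting), and to research procedures. Word AR and SAR so that it is clear which item each refers to.
3. In 8.2, align the causality step and the REDCap entry trigger with those definitions, and replace SR with a defined term. The sponsor needs to say which category was meant.

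The cost is a wording change in two sections and one added relatedness field, with a somewhat longer AE listing containing more minor events. It is best done before the first participant consents, because reclassifying logged events afterwards is harder.

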8.3 Responsibilities

ET workers and researchers:

- Record AEs, SAEs, and safeguarding concerns in the Safeguarding Log
- Notify the CIs that a new concern or incident has been added to the Log

CI or their delegate:

- Maintain the Safeguarding Log
- Review concerns or incidents added to the Safeguarding Log
- Ensure concerns or incidents are added to participants' notes on SystemOne as required
- Use experience and judgement to assign causality and determine actions required
- Ensure that all SAEs are recorded and reported to PenCTU and the Sponsor
- Ensure that actions decided on are taken
- Report safety information to the DMEC and TSC

DMEC and TSC:

- Conduct periodic reviews of safety information
- Liaise with one another regarding safety issues

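### Section 8.1 sets a stricter causality test for a Serious Adverse Reaction than for an Adverse Reaction, so a possibly related serious event is an SAE and an AR but not a SAR

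*Protocol*

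**What the plan says.** The definitions table in Protocol section 8.1 has four terms.

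- An AE is an unfavourable or unintended event "temporally associated with the intervention, whether or not it is related to that intervention". It has no upper limit on severity.
- For an AR, the CIs must judge that the AE "has the potential to be related to the intervention (i.e., its relationship to the intervention cannot be ruled out").
- An SAE is identified by its consequences, such as death, threat to life, hospitalisation or lasting disability.
- A SAR is "A SAE that, in the opinion of the CI, is believed with reasonable probability to be due to the intervention".

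Section 8.2 then describes how the terms are used. The CIs review each logged incident to "determine if there is a causal relationship between the incident and the study (i.e., if it is an AR or SAR") and to decide whether more needs to be done. The text adds: "This includes determining if the incident needs to be escalated as an SAR". The data-entry rule follows: "If an incident is determined to be an AR or SR, it must be entered into REDCap within 24 hours", counted from when the team learns of it. SR is defined neither in section 8.1 nor in the abbreviations list. On notification, section 8.2 says: "The sponsor will be automatically notified when an SAE is entered".

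Section 8.3 gives the CI or delegate the duty to "Ensure that all SAEs are recorded and reported to PenCTU and the Sponsor", and to pass safety information to the DMEC and TSC, which review it periodically.

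**The concern.** The usual logic of these four terms is a two-by-two layout: serious or not, related or not. A SAR should then be the overlap of SAE and AR. Here the step from AR to SAR changes two things at once. It adds seriousness, and it also raises the causality test from a link that cannot be excluded to one believed with reasonable probability. The label for the more harmful events therefore needs stronger belief in causation, and the protocol gives no reason for this.

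At stake is how related serious events are labelled. The DMEC may recommend stopping on safety grounds, and findings from this trial feed the decision on a full RCT. If related serious events reach the committees under the SAR label, those judged possibly related would not be among them, although the same protocol treats them as reactions.

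**Working it through.** The protocol states no figure on this point, so the check sets the definitions against the procedure.

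**Step 1. Can a serious event be an AR?** Yes, taking an SAE to be a kind of AE. The AE definition has no severity ceiling, and section 8.2 itself speaks of SAEs unrelated to the intervention, so SAE status does not presuppose causation. The AR definition covers any severity.

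**Step 2. Classify a serious event by the CI's view of causation, using section 8.1 as written.**

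| Judgement on the link to the intervention | SAE | AR | SAR |
|---|---|---|---|
| (a) Ruled out | Yes | No | No |
| (b) Cannot be ruled out, not thought reasonably probable | Yes | Yes | No |
| (c) Thought reasonably probable | Yes | Yes | Yes |

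Row (b) is the gap. These events are serious and are reactions by the protocol's own definition, yet they are not serious reactions.

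**Step 3. Compare with section 8.2.** That section describes one judgement, whether a causal relationship exists, and lets it decide AR or SAR status. If causality is a single yes/no answer, only seriousness can separate an AR from a SAR, and row (b) should carry the SAR label. Section 8.2 states no degree of belief, so it cannot say which of the two tests in section 8.1 applies. Nothing in sections 8.1 to 8.3 says that a serious AR is a SAR. The data-entry rule does not help, because its second term, SR, is undefined.

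**Step 4. Trace what happens to a row (b) event.**

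- REDCap entry within 24 hours: applies, because the event is an AR.
- Automatic notice to the sponsor: applies once it is entered as an SAE.
- Reporting to PenCTU and the sponsor: applies, because section 8.3 covers all SAEs whatever the causality.
- Safety information to the DMEC and TSC: applies in general terms, with no stated layout.
- Escalation as a SAR: does not apply, because the definition is not met.

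**Step 5. Size of the undercount.** Let S be the number of serious events that meet the AR test (rows b and c) and P the number thought reasonably probable (row c). As written, the SAR count is P. With one causality standard it is S. The difference is S − P, the number of row (b) events, which lies between 0 and S. The protocol gives no expected number of serious events and no split by causality, so the difference cannot be narrowed further.

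**The case against.** The strongest reply is that no specified reporting step depends on the SAR label. A row (b) event is entered within 24 hours as an AR, the sponsor is told when it is entered as an SAE, and all SAEs go to PenCTU and the sponsor. Section 9.3 adds weekly checks that SAE forms are complete, and section 9.2 has adverse events summarised descriptively. Sections 8.2 and 8.3 name no recipient, deadline or form that belongs to SARs alone. The progression criteria in section 2.2 contain no safety threshold. One can also argue that the single judgement in section 8.2 shows what was meant, and that the table is merely loosely worded.

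Most of this stands, and it rules out several stronger inferences that a reader might draw.

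- That possibly related serious events go unreported. The duties just listed contradict this.
- That the trial could show no SARs by definition and so confirm its view of ET as very low risk. The protocol plans no such argument: its statement about low risk is a starting premise, no SAR rate is specified, and events in row (c) would still be SARs.
- That most serious events would fall in the gap. The protocol gives no basis for this; section 8.2 anticipates events unrelated to the intervention, which belong in row (a).
- That the contrast is between serious and non-serious reactions. The AR definition covers all severities, which is why a serious event can be an AR without being a SAR.

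The reply does not remove the conflict. If one causal test was meant, the table contradicts it. If two were meant, section 8.2 does not say so. Whoever classifies an event has to choose, and the written SAR definition leads to the narrower label.

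**Conclusion.** The definitions are wrong as written, and the point is minor. Section 8.1 applies two causality standards where section 8.2 describes one judgement. A serious event whose link to ET is possible but not reasonably probable is excluded from the SAR category and from the decision to escalate as a SAR.

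The consequence is inconsistent classification and a possible undercount of related serious events in what the DMEC and TSC see. Two assumptions carry this. The first is that an SAE is a kind of AE, which the table implies without stating. The second is that summaries for the committees identify related serious events by the SAR label; the protocol does not say how they are laid out. If the summaries instead list every SAE with its causality judgement, the undercount disappears and only the inconsistent wording remains. No effect estimate or progression decision is touched.

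**What to change.** Reconcile sections 8.1 and 8.2 to one causality standard:

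1. In section 8.1, define a SAR as an AR that also meets one of the SAE seriousness criteria, so that seriousness alone separates the two terms.
2. In section 8.2, replace the undefined SR with SAR, and base the escalation decision on the revised definition.
3. Use the same definition in safety summaries for the DMEC and TSC.

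The cost is a one-sentence change to a definition, a one-word correction, and a check that the causality field on the eCRF matches. The only downside is that the SAR count may be slightly higher. The change is best made before the first consent, when the safety reporting period opens, so that all events are classified under one rule.
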